### **13.4 Quality Control**

The Quality Control steps will be defined in the Datasets, Tables, Listings, Figures QC Plan.

## 14 SAS Code

### 14.1 Comparison of Two Proportions Using 2-Sample Z Test

```
PROC FREQ DATA = <dataset>;  
    TABLES trt01pn*Response / RISKDIFF (CL=(WALD) COLUMN=2);  
    WHERE <population> = "Y" and ATPT = <timepoint>;  
RUN;
```

#### Notes:

- TRT01PN represents the treatment arm, incorporating the following ordering: 1=CUSA-081, 2=Placebo and 3=Alteplase;
- Response represents the treatment success indicator (1=Yes, 0=No).
- The Chi-square statistic corresponds to the square of the Z-statistics (so the p-value for Table 14.2.1.1.1 corresponds to the Chi-square p-value).

### 14.2 Kaplan-Meier Estimates

```
PROC LIFETEST data=<dataset> timelist=(0 5 10 15 20 25 30) alpha=0.05;  
    TIME time*censor(1);  
    STRATA trt01pn;  
RUN;
```

#### Notes:

- Time represents the time to event or time to censoring variable;
- Censor represents the censoring indicator (0=event, 1=censored);
- TRT01PN represents the treatment arm, incorporating the following ordering: 1=CUSA-081, 2=Placebo and 3=Alteplase;

### 14.3 Cox Proportional Hazards Model

```
PROC PHREG data=<dataset>;  
    CLASS trt01pn / param=glm order=internal;  
    MODEL time*censor(1) = trt01pn;  
  
    CONTRAST 'CUSA-081 vs Placebo'    trt01pn 1 -1 0 / estimate=exp e;  
    CONTRAST 'CUSA-081 vs Alteplase'   trt01pn 1 0 -1 / estimate=exp e;  
    CONTRAST 'Alteplase vs Placebo'    trt01pn 0 -1 1 / estimate=exp e;  
RUN;
```

#### Notes:

- Time represents the time to event or time to censoring variable;
- Censor represents the censoring indicator (0=event, 1=censored);
- TRT01PN represents the treatment arm, incorporating the following ordering: 1=CUSA-081, 2=Placebo and 3=Alteplase;

## 14.4 Logistic Regression Model

```
PROC LOGISTIC data=<dataset>;  
  CLASS trt01pn (ref="2") agec region / param=glm;  
  MODEL resp = trt01pn agec region;  
  LSMEANS trt01pn / e diff oddsratio cl;  
RUN;
```

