## 9.1 Primary Efficacy Variable

The primary efficacy variable is the percentage of subjects who have treatment success following a single instillation of study drug (CUSA-081, alteplase, or placebo) with a dwell time up to 90 minutes. Treatment success will be derived as mentioned in Section 7.3.

Protocol violations and any other intercurrent events will be ignored for analyses performed on the FAS, which target a treatment policy estimand. Subjects with important protocol deviations will be excluded from analyses based on the PPS.

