### **Sensitivity Analysis**

A sensitivity analysis will be performed on the primary efficacy endpoint using a logistic regression model with age (<18, ≥18-<65, ≥65-<85, ≥85 years) and region (US vs Non-US) as factors. The odds-ratio, 95% confidence interval for the odds-ratio and the p-value will be displayed for each treatment group comparison (See Section 14.4).

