### Notes:

- TRT01PN represents the treatment arm, incorporating the following ordering: 1=CUSA-081, 2=Placebo and 3=Alteplase;
- AGE C represents the age in category (<18, ≥18-<65, ≥65-<85, ≥85 years).
- REGION represents the country in category (US vs Non-US).

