Table 14.2.1.5.1	Summary and Sensitivity Analysis of Proportion of Subjects with Treatment Success Up to 90 Minutes Following a Single Instillation of Study Drug – Logistic Regression Model (Full Analysis Set)	ANT004	
 
- Timepoints to be presented: 30, 60 and 90 mins.
 
- Do not display the row “Overall”.
 
- Only the following comparisons will be performed: CUSA-081 vs Placebo and CUSA-081 vs Alteplase.
 
- Add the columns ‘n Success’ and ‘Proportion of Treatment Success (95% CI)’ after ‘n’ column.
 
	
Source: Listing 16.2.6.1
 
Footnotes: [1] n corresponds to the number of subjects included in the analysis. [2] ‘n Success’ corresponds to the number of subjects with treatment success. [3] P-value, odds ratio and its 95% confidence intervals are based on a logistic regression model with age and region as factors.

Table 14.2.1.5.2	Summary and Sensitivity Analysis of Proportion of Subjects with Treatment Success Up to 90 Minutes Following a Single Instillation of Study – Logistic Regression Model Drug (Intention-to-Treat Set)	ANT004	Same as Table 14.2.1.5.1	Same as Table 14.2.1.5.1

Table Number	Table Title	Template Code	Notes	Footnotes/Source Listing Number
Table 14.2.1.5.3	Summary and Sensitivity Analysis of Proportion of Subjects with Treatment Success Up to 90 Minutes Following a Single Instillation of Study Drug – Logistic Regression Model (Per-Protocol Set)	ANT004	Same as Table 14.2.1.5.1	Same as Table 14.2.1.5.1

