Table 14.2.2.4.5	Summary and Statistical Analysis of Proportion of Subjects with Treatment Success Up to 180 Minutes Following Two Instillations of Study Drug by Country (Full Analysis Set)	ANT007	Same as Table 14.2.2.4.1	Same as Table 14.2.2.4.1
Table 14.2.2.4.6	Summary and Statistical Analysis of Proportion of Subjects with Treatment Success Up to 180 Minutes Following Two Instillations of Study Drug by Region (Full Analysis Set)	ANT007	Same as Table 14.2.2.4.1	Same as Table 14.2.2.4.1
Table 14.2.2.4.7	Summary and Statistical Analysis of Proportion of Subjects with Treatment Success Up to 180 Minutes Following Two Instillations of Study Drug by Body Mass Index (Full Analysis Set)	ANT007	Same as Table 14.2.2.4.1	Same as Table 14.2.2.4.1
Table 14.2.2.4.8	Summary and Statistical Analysis of Proportion of Subjects with Treatment Success Up to 180 Minutes Following Two Instillations of Study Drug by Type of CVAD (Full Analysis Set)	ANT007	Same as Table 14.2.2.4.1	Same as Table 14.2.2.4.1
Table 14.2.2.4.9	Summary and Statistical Analysis of Proportion of Subjects with Treatment Success Up to 180 Minutes Following Two Instillations of Study Drug by Number of Lumens (Full Analysis Set)	ANT007	Same as Table 14.2.2.4.1	Same as Table 14.2.2.4.1

Table Number	Table Title	Template Code	Notes	Footnotes/Source Listing Number
Table 14.2.2.4.10	Summary and Statistical Analysis of Proportion of Subjects with Treatment Success Up to 180 Minutes Following Two Instillations of Study Drug by Where and Whom CVAD Identified as Dysfunctional (Full Analysis Set)	ANT007	Same as Table 14.2.2.4.1	Same as Table 14.2.2.4.1
Table 14.2.2.4.11	Summary and Statistical Analysis of Proportion of Subjects with Treatment Success Up to 180 Minutes Following Two Instillations of Study Drug by Duration of CVAD Dysfunction (Full Analysis Set)	ANT007	Same as Table 14.2.2.4.1	Same as Table 14.2.2.4.1
Table 14.2.2.5.1	Summary and Sensitivity Analysis of Proportion of Subjects with Treatment Success Up to 180 Minutes Following Two Instillations of Study Drug - Logistic Regression Model (Full Analysis Set)	ANT004	- Same as Table 14.2.1.5.1. - Timepoints to be presented: 120, 150 and 180 mins.	Same as Table 14.2.1.5.1
Table 14.2.2.5.2	Summary and Sensitivity Analysis of Proportion of Subjects with Treatment Success Up to 180 Minutes Following Two Instillations of Study Drug - Logistic Regression Model (Intention-to-Treat Set)	ANT004	Same as Table 14.2.2.5.1	Same as Table 14.2.2.5.1

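### The logistic code in SAP 14.4 names no event level and leaves `resp` undefined; with 0/1 coding and the SAS default it would report odds ratios of failure in tables titled for treatment success

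*SAP*

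**What the plan says.** SAP 9.1 introduces the model and sends the reader to 14.4 for the code: "A sensitivity analysis will be performed on the primary efficacy endpoint using a logistic regression model with age" (and region). The endpoint is success: "The primary efficacy variable is the percentage of subjects who have treatment success following a single instillation of study drug".

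The model statement in 14.4 is "MODEL resp = trt01pn agec region". The procedure statement names only the input dataset. The notes below it cover the treatment variable, the age category and, last, region: "REGION represents the country in category (US vs Non-US". There is no entry for `resp`.

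The one response coding in the SAP is in the notes to 14.1: "Response represents the treatment success indicator (1=Yes, 0=No". It applies to a variable called `Response`.

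The results go into Tables 14.2.1.5.1 to 14.2.1.5.3 (30, 60 and 90 minutes) and 14.2.2.5.1 to 14.2.2.5.3 (120, 150 and 180 minutes). The second set is titled "Proportion of Subjects with Treatment Success Up to 180 Minutes Following Two Instillations of Study Drug - Logistic Regression Model". The footnote on the odds ratio, reused across all six tables, reads: "P-value, odds ratio and its 95% confidence intervals are based on a logistic regression model with age and region as factors".

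**The concern.** Nothing in 14.4, 9.1 or the table footnotes says whether the odds ratio is for success or for failure. The titles point to success. The printed code, read with the SAP's own 0/1 coding and the usual default of the procedure, points to failure.

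The other code in Section 14 does fix the outcome level. 14.1 requests `COLUMN=2`, which selects success when 0 sorts before 1. 14.3 uses `censor(1)`, and its notes say which value is the event. The logistic model is the only outcome analysis there without such a statement.

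If failure were modelled, an arm with better patency would show an odds ratio below 1 in a table titled for success, and no footnote would warn the reader. A second programmer checking against the same code could reproduce the same direction.

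**Working it through.** **The plan's own figure.** The documents state no odds ratio, so there is none to reproduce. The check compares passages and then measures what a reversal would do.

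**Which level the code models**
- SAP 14.4: no event option, no descending option, `resp` undefined.
- SAP 14.1 notes: success = 1, no success = 0.
- SAP 13.1: the software is SAS 9.4.
- Assumption: without an event option, PROC LOGISTIC models the lowest ordered level of a binary response. This is general knowledge of the procedure. It is not in the documents and was not tested in SAS.

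| Coding (success, failure) | Lowest level | Code models |
|---|---|---|
| 1, 0 | 0 | failure |
| Yes, No | No | failure |
| Y, N | N | failure |
| 1, 2 | 1 | success |

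Only the last coding gives the intended direction, and the SAP does not state it.

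**Size for each comparison**

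Rates come from SAP 5: placebo 20%, and 75% in both active arms for the non-inferiority calculation. Others are derived: 20 + 35 = 55%; 75 + 10 = 85%; 75 − 10 = 65% (at the margin). Reading the 10-point difference as 85% vs 75% fits the plan: 450 and 300 subjects then give 92.2% power against the stated 92%, whereas 75% vs 65% gives 83.7%.

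Odds ratio of success = [p1/(1 − p1)] / [p2/(1 − p2)]. The odds ratio of failure is its reciprocal.

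| CUSA-081 vs comparator | Success (intended) | Failure (code as printed) |
|---|---|---|
| 55% vs 20% (placebo) | 1.222/0.25 = 4.89 | 0.205 |
| 85% vs 75% (alteplase) | 5.667/3 = 1.89 | 0.53 |
| 65% vs 75% (alteplase) | 1.857/3 = 0.62 | 1.62 |
| 75% vs 75% (alteplase) | 3/3 = 1.00 | 1.00 |

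In the third row the worse arm would appear to be the better one.

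**Fitted check.** A logistic model with treatment terms only was fitted in Python to whole-subject counts:
- 248/450 vs 10/50: 4.91 (95% CI 2.40 to 10.06) for success; 0.204 (0.099 to 0.417) for failure.
- 383/450 vs 225/300: 1.91 (1.32 to 2.75) for success; 0.525 (0.363 to 0.759) for failure.

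The p-values agree in each pair. The small differences from the table come from rounding to whole subjects.

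A model also containing age group and region was fitted to simulated 9:1:6 data (success rates 75/20/75%) with total N of 160, 416 and 841. The product of the success and failure odds ratios was 1.000 for both comparisons at every size. The relation does not depend on sample size, so the early termination recorded in SAP 12 does not alter it.

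**How many estimates.** The table notes limit the output: "Only the following comparisons will be performed: CUSA-081 vs Placebo and CUSA-081 vs Alteplase". So 6 tables × 3 timepoints × 2 comparisons = 36 odds ratios.

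**The case against.** The inversion needs two facts that the documents do not supply: the software default, and that `resp` is coded like `Response`. The fitted checks cannot settle either; they only confirm that swapping event and non-event inverts an odds ratio.

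The code in 14.4 is also a skeleton. It has a dataset placeholder and no selection of timepoint or analysis set, so a programmer must complete it in any case and might add the event level then. The code in 14.1 is abbreviated too: its notes take the p-value from a chi-square statistic that the code does not request.

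The intended outcome is plain from 9.1 and the titles. The same tables must show the number and proportion of successes in each arm, so 65% vs 75% beside an odds ratio of 1.62 would look wrong. Against placebo the reversal would be obvious.

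Much of this stands. The inversion is conditional, and the impact is small. SAP 7.4 also says that no efficacy analysis will be covariate-adjusted, so this model carries no special weight. But no passage sets the direction in the code, defines `resp`, or tells the reader which outcome the odds ratio describes. Against alteplase, where similar rates are expected, a modest reversed odds ratio is easier to miss.

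**Conclusion.** The point holds. That 14.4 names no event level, leaves `resp` undefined and leads to tables that do not state the direction of the odds ratio follows from the documents alone. With the SAP's only response coding and the usual PROC LOGISTIC default, the printed code contradicts 9.1 and would invert all 36 odds ratios. If `resp` were coded with success as the lowest level, none would be inverted.

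Severity is low. This is a sensitivity analysis outside the hierarchical tests. The two-sided p-values, the primary z test with its Wald interval, and the non-inferiority decision rule do not change.

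**What to change.** - In the notes to SAP 14.4, define `resp` as the treatment success indicator, with 1 for success and 0 otherwise.
- Change the model statement to `MODEL resp(event='1') = trt01pn agec region;`.
- Add one footnote to Tables 14.2.1.5.1 to 14.2.1.5.3 and 14.2.2.5.1 to 14.2.2.5.3: the odds ratio is for treatment success, and a value above 1 favours the first-named arm.

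The cost is one note, one code option and one shared footnote. Data, design and method stay as they are, and the direction no longer depends on the programmer's coding or a software default.

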### Notes:

- TRT01PN represents the treatment arm, incorporating the following ordering: 1=CUSA-081, 2=Placebo and 3=Alteplase;
- AGE C represents the age in category (<18, ≥18-<65, ≥65-<85, ≥85 years).
- REGION represents the country in category (US vs Non-US).

## 14.5 Conditional Power

Of note, the interim analysis will not be conducted as a result of the early stopping of the study. The below text in this section is maintained for consistency with the protocol and to maintain a record of the original plan. See Section 12 for additional details.

Create a dataset with a single record and the following variables included as defined below:

- $n_{i1}$  = number of subjects in CUSA-081 group at interim
- $n_{i2}$  = number of subjects in alteplase group at interim
- $n1$  = 473 (This is the total number of subjects in CUSA-081 group planned at the end of the trial)
- $n2$  = 315 (This is the number of subjects in alteplase group planned at the end of the trial)
- $e_{i1}$  = number of successes in CUSA-081 group at interim
- $e_{i2}$  = number of successes in alteplase group at interim

Next, create a new dataset, based on the prior dataset:

```
DATA <dataset name>;  
  SET <name of prior dataset>;  
  alpha = 0.025;  
  NIMarg = -0.1;
```

```
* Information fraction;  
i=(n_i1+n_i2)/(n1+n2);
```

```
* Interim proportions;  
p_i1=e_i1/n_i1;  
p_i2=e_i2/n_i2;
```

```
* Interim difference between proportions, SE and test statistic (H0: diff ≤ NI Margin;  
* H1: diff > NI Margin);  
diff_i=p_i1-p_i2;
```

---

```
se_i=sqrt( (p_i1*(1-p_i1)/n_i1) + (p_i2*(1-p_i2)/n_i2) );  
z_i=(diff_i-(NIMarg))/se_i;
```

```
* Conditional power CP(d) formula in Gallo, Mao, Shih, Alternative views on;  
* setting clinical trial futility criteria, Journal of Biopharmaceutical Statistics 2014;  
cp=probnorm(-1/sqrt(1-i)*(probit(1-alpha) - z_i/sqrt(i)));  
RUN;
```

## 16 List of Tables, Listings and Figures

### 16.1 Tables

The SAS output for the analyses included in the flagged (\*\*\*) tables below will be provided as separate documents for internal use only and not for inclusion into the CSR.

Table Number	Table Title	Template Code	Notes	Footnotes/Source Listing Number
Table 14.1.1.1	Screen Failures (Enrolled Set)	DST001	Overall column should be displayed.	Source: Listing 16.2.1.1
Table 14.1.1.2	Disposition by Treatment (Intention-to-Treat Set)	DST002	
 
- Overall column should be displayed.
 
- Replace 'Primary Reason for Discontinuation' by 'Primary Reason for Study Discontinuation'.
 
- 'Not Treated', 'Completed the Treatment Period' and 'Discontinued the Treatment Period' sections with the 'Primary Reason of Treatment Period Discontinuation' should be also displayed.
 
	Source: Listing 16.2.1.2  Footnotes: [1] Treatment period corresponds to Visit 1.
Table 14.1.1.3	Disposition by Country (Intention-to-Treat Set)	DST004	
 
- Overall column should be displayed.
 
- Include 'Discontinued from Treatment' and 'Discontinued from Study'.
 
	Source: Listing 16.2.1.2
Table 14.1.1.4	Disposition by Site (Intention-to-Treat Set)	DST004	
 
- Same as Table 14.1.1.4
 
- Display "Country/Site" and sort by country and by site number.
 
	Same as Table 14.1.1.4
Table 14.1.1.5	Attendance at Study Visits and CVAD Assessment Timepoints (Intention-to-Treat Set)	SVT001	
 
- Overall column should be displayed.
 
- Within Visit, timepoints (based on CVAD page in eCRF) to be added.
 
- Prior to achieving treatment success, a subject is counted in a visit/timepoint if the visit or CVAD assessment at the time point has been performed. Following achievement of treatment success, a subject is counted in a visit/timepoint if they have not discontinued the study.
 
	Source: Listings 16.2.1.4 and 16.2.6.1

Table Number	Table Title	Template Code	Notes	Footnotes/Source Listing Number
Table 14.1.1.6	Important Protocol Deviations (Full Analysis Set)	DVT001	
 
- Display the summary of “At Least One Deviation Excluding from Per-Protocol Set”.
 
- Display the summary of “At Least One Deviation” (i.e. all important protocol deviations regardless if leading or not to exclusion from PP Set).
 
	Source: Listing 16.2.2.2
Table 14.1.1.7	Analysis Sets (Intention-to-Treat Set)	DST005	
 
- Overall column should be displayed.
 
- Populations to be displayed: FAS, Safety, PP Sets.
 
- Display the full names and abbreviations in brackets.
 
	Source: Listing 16.2.3.1  Footnotes: [1] Intention-to-Treat Analysis Set (ITT) includes all randomized subjects regardless if they received treatment with study drug. [2] Full Analysis Set (FAS) includes all randomized subjects who receive at least one dose of study drug, and with at least one available evaluation of efficacy after baseline (i.e. at least one CVAD assessment after study drug administration). [3] Safety Set (SS) includes all randomized subjects who receive at least one dose of study drug. [4] Per-Protocol Analysis Set (PPS) includes all subjects from the ITT Set without any important protocol deviations.

Table Number	Table Title	Template Code	Notes	Footnotes/Source Listing Number
Table 14.1.2.1	Demographic and Baseline Characteristics (Full Analysis Set)	DMT001	
 
- Overall column should be displayed.
 
- Variables to be summarized: Age, Age Category, Gender, Race (categories as per CRF to be displayed), Ethnicity (categories as per CRF to be displayed), Height, Weight, BMI, SBP, DBP, HR and Urine Pregnancy Test (only for females).
 
- All categories should be displayed even if empty.
 
	Source: Listing 16.2.4.1
Table 14.1.2.2	Demographic and Baseline Characteristics (Safety Set)	DMT001	Same as Table 14.1.2.1	Same as Table 14.1.2.1
Table 14.1.2.3	Demographic and Baseline Characteristics (Intention-to-Treat Set)	DMT001	Same as Table 14.1.2.1	Same as Table 14.1.2.1
Table 14.1.2.4	Demographic and Baseline Characteristics (Per-Protocol Set)	DMT001	Same as Table 14.1.2.1	Same as Table 14.1.2.1
Table 14.1.3.1	CVAD History (Full Analysis Set)	BLT001	
 
- Overall column should be displayed.
 
- Variables to be summarized: 
 
– Time Between Screening CVAD Assessment and First Drug Administration (Hours)
 
– CVAD Type
 
– CVAD Lumen (Single lumen, Multi-Lumen: 2, Multi-Lumen: 3, Multi-Lumen: 4)
 
– Number of Lumens
 
– Indication for Insertion [1]
 
– Duration CVAD Was Dysfunctional (Hours)
 
– When and By Whom the CVAD Was Identified as Dysfunctional
 
 
 
	Source: Listing 16.2.4.2  Footnotes: [1] Several indications may be possible for a subject.
Table 14.1.3.2	CVAD History (Safety Set)	BLT001	Same as Table 14.1.3.1	Same as Table 14.1.3.1
Table 14.1.3.3	CVAD History (Intention-to-Treat Set)	BLT001	Same as Table 14.1.3.1	Same as Table 14.1.3.1
Table 14.1.3.4	CVAD History (Per-Protocol Set)	BLT001	Same as Table 14.1.3.1	Same as Table 14.1.3.1

Table Number	Table Title	Template Code	Notes	Footnotes/Source Listing Number
Table 14.1.4.1	Medical and Surgical History (Safety Set)	MHT001	- Overall column should be displayed. - Replace <Condition/Procedure> by 'Medical History'.	Source: Listing 16.2.4.3  Footnotes: [1] System Organ Class and Preferred Term are coded using MedDRA Version xx.x.
Table 14.1.5.1	Concomitant Diseases (Safety Set)	MHT001	- Overall column should be displayed. - Replace <Condition/Procedure> by 'Concomitant Disease'.	Source: Listing 16.2.4.4  Footnotes: [1] System Organ Class and Preferred Term are coded using MedDRA Version xx.x.
Table 14.1.6.1	Prior Procedures (Safety Set)	MHT001	Overall column should be displayed.	Source: Listing 16.2.4.5  Footnotes: [1] System Organ Class and Preferred Term are coded using MedDRA Version xx.x.
Table 14.1.7.1	Maintained Procedures (Safety Set)	MHT002	Overall column should be displayed.	Same as Table 14.1.6.1
Table 14.1.8.1	Concomitant Procedures (Safety Set)	MHT002		Same as Table 14.1.6.1
Table 14.1.9.1	Prior Medications (Safety Set)	CMT001	Overall column should be displayed.	Source: Listing 16.2.4.6  Footnotes: [1] ATCs and Preferred Name are coded using WHO-DD XXXX 20XX.
Table 14.1.10.1	Maintained Medications (Full Analysis Set)	CMT001	Same as Table 14.1.9.1	Same as Table 14.1.9.1
Table 14.1.10.2	Maintained Medications (Safety Set)	CMT001	Same as Table 14.1.9.1	Same as Table 14.1.9.1
Table 14.1.11.1	Concomitant Medications (Full Analysis Set)	CMT002		Same as Table 14.1.9.1

Table Number	Table Title	Template Code	Notes	Footnotes/Source Listing Number
Table 14.1.11.2	Concomitant Medications (Safety Set)	CMT002		Same as Table 14.1.9.1
Table 14.2.1.1.1	Summary and Statistical Analysis of Proportion of Subjects with Treatment Success Up to 90 Minutes Following a Single Instillation of Study Drug (Full Analysis Set)	ANT007	
 
- Replace “Adjusted Mean” with “Proportion of Treatment Success (95% CI)” and “Adjusted Mean difference” with “Difference in Proportions (95% CI)”.
 
- Do not display Parameter column.
 
- Replace Study Day by Timepoint.
 
- Timepoints to be presented: 30, 60 and 90 mins.
 
- Add column for P-value for all the treatment comparison at all timepoints as last column.
 
- In the column Treatment and after all treatments listed, add the different comparisons: CUSA-081 vs Placebo, CUSA-081 vs Alteplase, Alteplase vs Placebo.
 
- Replace ‘n’ by ‘n Success’.
 
	
Source: Listing 16.2.6.1
 
Footnotes: [1] ‘n Success’ corresponds to the number of subjects with treatment success. [2] The 95% confidence intervals of proportions and difference of proportions are based on Wald method. [3] The p-value is based on a 2-sample Z test for proportions. [4] Percentages are based on the number of subjects in the treatment group.

Table 14.2.1.1.2 ***	SAS Output: Summary and Statistical Analysis of Proportion of Subjects with Treatment Success Up to 90 Minutes Following a Single Instillation of Study Drug (Full Analysis Set)		Raw SAS output	
Table 14.2.1.2	Summary and Sensitivity Analysis of Proportion of Subjects with Treatment Success Up to 90 Minutes Following a Single Instillation of Study Drug (Intention-to-Treat Set)	ANT007	
Same as Table 14.2.1.1.1
 
The randomized but non-treated subjects will be considered as non-responders.
	Same as Table 14.2.1.1.1
Table 14.2.1.3.1	Summary and Sensitivity Analysis of Proportion of Subjects with Treatment Success Up to 90 Minutes Following a Single Instillation of Study Drug (Per-Protocol Set)	ANT007	Same as Table 14.2.1.1.1	Same as Table 14.2.1.1.1

Table Number	Table Title	Template Code	Notes	Footnotes/Source Listing Number
Table 14.2.1.3.2 ***	SAS Output: Summary and Sensitivity Analysis of Proportion of Subjects with Treatment Success Up to 90 Minutes Following a Single Instillation of Study Drug (Per-Protocol Set)		Raw SAS output	
Table 14.2.1.4.1	Summary and Statistical Analysis of Proportion of Subjects with Treatment Success Up to 90 Minutes Following a Single Instillation of Study Drug by Age (Full Analysis Set)	ANT007	
Same as Table 14.2.1.1.1
 
 
- Add a subgroup title for each age category.
 
- N should display the number of subjects within the subgroup category.
 
- Categories with fewer than 1 randomized patients are excluded from this analysis.
 
- For the treatment comparison rows, if there are <3 subjects in one of the 2 arms compared, then the columns “Difference in Proportions (95% CI)” and “P-Value” will be left empty.
 
- Footnotes [5] and [6] to be displayed only if applicable to the output (it will be displayed on all pages even if not applicable to a specific subgroup).
 
	
Source: Listing 16.2.6.1
 
Footnotes: [1] ‘n Success’ corresponds to the number of subjects with treatment success. [2] The 95% confidence intervals of proportions and difference of proportions are based on Wald method. [3] The p-value is based on a 2-sample Z test for proportions. [4] Percentages are based on the number of subjects in the treatment group and in the subgroup. [5] Comparisons with less than 3 subjects in one of the treatment group will not be performed. [6] NE = Not estimable.

Table 14.2.1.4.2	Summary and Statistical Analysis of Proportion of Subjects with Treatment Success Up to 90 Minutes Following a Single Instillation of Study Drug by Sex (Full Analysis Set)	ANT007	Same as Table 14.2.1.4.1	Same as Table 14.2.1.4.1

Table Number	Table Title	Template Code	Notes	Footnotes/Source Listing Number
Table 14.2.1.4.3	Summary and Statistical Analysis of Proportion of Subjects with Treatment Success Up to 90 Minutes Following a Single Instillation of Study Drug by Race (Full Analysis Set)	ANT007	Same as Table 14.2.1.4.1	Same as Table 14.2.1.4.1
Table 14.2.1.4.4	Summary and Statistical Analysis of Proportion of Subjects with Treatment Success Up to 90 Minutes Following a Single Instillation of Study Drug by Ethnicity (Full Analysis Set)	ANT007	Same as Table 14.2.1.4.1	Same as Table 14.2.1.4.1
Table 14.2.1.4.5	Summary and Statistical Analysis of Proportion of Subjects with Treatment Success Up to 90 Minutes Following a Single Instillation of Study Drug by Country (Full Analysis Set)	ANT007	Same as Table 14.2.1.4.1	Same as Table 14.2.1.4.1
Table 14.2.1.4.6	Summary and Statistical Analysis of Proportion of Subjects with Treatment Success Up to 90 Minutes Following a Single Instillation of Study Drug by Region (Full Analysis Set)	ANT007	Same as Table 14.2.1.4.1	Same as Table 14.2.1.4.1
Table 14.2.1.4.7	Summary and Statistical Analysis of Proportion of Subjects with Treatment Success Up to 90 Minutes Following a Single Instillation of Study Drug by Body Mass Index (Full Analysis Set)	ANT007	Same as Table 14.2.1.4.1	Same as Table 14.2.1.4.1
Table 14.2.1.4.8	Summary and Statistical Analysis of Proportion of Subjects with Treatment Success Up to 90 Minutes Following a Single Instillation of Study Drug by Type of CVAD (Full Analysis Set)	ANT007	Same as Table 14.2.1.4.1	Same as Table 14.2.1.4.1
Table 14.2.1.4.9	Summary and Statistical Analysis of Proportion of Subjects with Treatment Success Up to 90 Minutes Following a Single Instillation of Study Drug by Number of Lumens (Full Analysis Set)	ANT007	Same as Table 14.2.1.4.1	Same as Table 14.2.1.4.1

Table Number	Table Title	Template Code	Notes	Footnotes/Source Listing Number
Table 14.2.1.4.10	Summary and Statistical Analysis of Proportion of Subjects with Treatment Success Up to 90 Minutes Following a Single Instillation of Study Drug by Where and Whom CVAD Identified as Dysfunctional (Full Analysis Set)	ANT007	Same as Table 14.2.1.4.1	Same as Table 14.2.1.4.1
Table 14.2.1.4.11	Summary and Statistical Analysis of Proportion of Subjects with Treatment Success Up to 90 Minutes Following a Single Instillation of Study Drug by Duration of CVAD Dysfunction (Full Analysis Set)	ANT007	Same as Table 14.2.1.4.1	Same as Table 14.2.1.4.1
Table 14.2.1.5.1	Summary and Sensitivity Analysis of Proportion of Subjects with Treatment Success Up to 90 Minutes Following a Single Instillation of Study Drug – Logistic Regression Model (Full Analysis Set)	ANT004	
 
- Timepoints to be presented: 30, 60 and 90 mins.
 
- Do not display the row “Overall”.
 
- Only the following comparisons will be performed: CUSA-081 vs Placebo and CUSA-081 vs Alteplase.
 
- Add the columns ‘n Success’ and ‘Proportion of Treatment Success (95% CI)’ after ‘n’ column.
 
	
Source: Listing 16.2.6.1
 
Footnotes: [1] n corresponds to the number of subjects included in the analysis. [2] ‘n Success’ corresponds to the number of subjects with treatment success. [3] P-value, odds ratio and its 95% confidence intervals are based on a logistic regression model with age and region as factors.

Table 14.2.1.5.2	Summary and Sensitivity Analysis of Proportion of Subjects with Treatment Success Up to 90 Minutes Following a Single Instillation of Study – Logistic Regression Model Drug (Intention-to-Treat Set)	ANT004	Same as Table 14.2.1.5.1	Same as Table 14.2.1.5.1

Table Number	Table Title	Template Code	Notes	Footnotes/Source Listing Number
Table 14.2.1.5.3	Summary and Sensitivity Analysis of Proportion of Subjects with Treatment Success Up to 90 Minutes Following a Single Instillation of Study Drug – Logistic Regression Model (Per-Protocol Set)	ANT004	Same as Table 14.2.1.5.1	Same as Table 14.2.1.5.1
Table 14.2.1.6	Outcome of Futility Analysis (Full Analysis Set)		
 
- This table is generated only for futility analysis.
 
- The table has 3 columns ‘CUSA-081 (N=xxx)’, ‘Alteplase (N=xxx)’, ‘CUSA-081 vs Alteplase’.
 
- Display the following rows:               
 
- Number of Subjects included in the Futility Analysis
 
- Proportion of Treatment Success at 90 mins at Futility Analysis (%)
 
- Difference in Proportions (95% CI)
 
- Conditional Power: (no result) 
 
– Information Level at Futility Analysis
 
– Z-statistic
 
– Conditional Power based on a planned total sample size of 788 Subjects included in the CUSA-081 and alteplase arms of the Full Analysis Set
 
 
 
 
 
 
Notes:
 
 
– The 3 first rows results are based on Table 14.2.1.1.1.
 
– Information Level corresponds to parameter <math>I</math> in Section 14.5).
 
– Z-statistics corresponds to parameter <math>z_I</math> in Section 14.5).
 
– Conditional Power corresponds to parameter CP(d) in Section 14.5).
 
– The conditional power is displayed with 1 additional digit compared to the threshold mentioned in the DMC Charter.
 
	
Source: Table 14.2.1.1.1
 
Footnotes: [1] The conditional power is computed assuming that the observed proportions of treatment success in each treatment group are the proportions observed for the full study.

Table Number	Table Title	Template Code	Notes	Footnotes/Source Listing Number
Table 14.2.2.1.1	Summary and Statistical Analysis of Proportion of Subjects with Treatment Success Up to 180 Minutes Following Two Instillations of Study Drug (Full Analysis Set)	ANT007	Same as Table 14.2.1.1.1  Timepoints to be presented: 120, 150 and 180 mins.	Same as Table 14.2.1.1.1
Table 14.2.2.1.2 ***	SAS Output: Summary and Statistical Analysis of Proportion of Subjects with Treatment Success Up to 180 Minutes Following Two Instillations of Study Drug (Full Analysis Set)		Raw SAS output	
Table 14.2.2.2	Summary and Sensitivity Analysis of Proportion of Subjects with Treatment Success Up to 180 Minutes Following Two Instillations of Study Drug (Intention-to-Treat Set)	ANT007	Same as Table 14.2.2.1.1	Same as Table 14.2.2.1.1
Table 14.2.2.3	Summary and Sensitivity Analysis of Proportion of Subjects with Treatment Success Up to 180 Minutes Following Two Instillations of Study Drug (Per-Protocol Set)	ANT007	Same as Table 14.2.2.1.1	Same as Table 14.2.2.1.1

Table Number	Table Title	Template Code	Notes	Footnotes/Source Listing Number
Table 14.2.2.4.1	Summary and Statistical Analysis of Proportion of Subjects with Treatment Success Up to 180 Minutes Following Two Instillations of Study Drug by Age (Full Analysis Set)	ANT007	
Same as Table 14.2.2.1.1
 
 
- Add a subgroup title for each age category.
 
- N should display the number of subjects within the subgroup category.
 
- Categories with fewer than 1 randomized patient are excluded from this analysis.
 
- For the treatment comparison rows, if there are <3 subjects in one of the 2 arms compared, then the columns “Difference in Proportions (95% CI)” and “P-Value” will be left empty.
 
- Footnotes [5] and [6] to be displayed only if applicable to the output.
 
	
Source: Listing 16.2.6.1
 
Footnotes: [1] ‘n Success’ corresponds to the number of subjects with treatment success. [2] The 95% confidence intervals of proportions and difference of proportions are based on Wald method. [3] The p-value is based on a 2-sample Z test for proportions. [4] Percentages are based on the number of subjects in the treatment group and in the subgroup. [5] Comparisons with less than 3 subjects in one of the treatment group will not be performed. [6] NE = Not estimable.

Table 14.2.2.4.2	Summary and Statistical Analysis of Proportion of Subjects with Treatment Success Up to 180 Minutes Following Two Instillations of Study Drug by Sex (Full Analysis Set)	ANT007	Same as Table 14.2.2.4.1	Same as Table 14.2.2.4.1
Table 14.2.2.4.3	Summary and Statistical Analysis of Proportion of Subjects with Treatment Success Up to 180 Minutes Following Two Instillations of Study Drug by Race (Full Analysis Set)	ANT007	Same as Table 14.2.2.4.1	Same as Table 14.2.2.4.1

Table Number	Table Title	Template Code	Notes	Footnotes/Source Listing Number
Table 14.2.2.4.4	Summary and Statistical Analysis of Proportion of Subjects with Treatment Success Up to 180 Minutes Following Two Instillations of Study Drug by Ethnicity (Full Analysis Set)	ANT007	Same as Table 14.2.2.4.1	Same as Table 14.2.2.4.1
Table 14.2.2.4.5	Summary and Statistical Analysis of Proportion of Subjects with Treatment Success Up to 180 Minutes Following Two Instillations of Study Drug by Country (Full Analysis Set)	ANT007	Same as Table 14.2.2.4.1	Same as Table 14.2.2.4.1
Table 14.2.2.4.6	Summary and Statistical Analysis of Proportion of Subjects with Treatment Success Up to 180 Minutes Following Two Instillations of Study Drug by Region (Full Analysis Set)	ANT007	Same as Table 14.2.2.4.1	Same as Table 14.2.2.4.1
Table 14.2.2.4.7	Summary and Statistical Analysis of Proportion of Subjects with Treatment Success Up to 180 Minutes Following Two Instillations of Study Drug by Body Mass Index (Full Analysis Set)	ANT007	Same as Table 14.2.2.4.1	Same as Table 14.2.2.4.1
Table 14.2.2.4.8	Summary and Statistical Analysis of Proportion of Subjects with Treatment Success Up to 180 Minutes Following Two Instillations of Study Drug by Type of CVAD (Full Analysis Set)	ANT007	Same as Table 14.2.2.4.1	Same as Table 14.2.2.4.1
Table 14.2.2.4.9	Summary and Statistical Analysis of Proportion of Subjects with Treatment Success Up to 180 Minutes Following Two Instillations of Study Drug by Number of Lumens (Full Analysis Set)	ANT007	Same as Table 14.2.2.4.1	Same as Table 14.2.2.4.1

Table Number	Table Title	Template Code	Notes	Footnotes/Source Listing Number
Table 14.2.2.4.10	Summary and Statistical Analysis of Proportion of Subjects with Treatment Success Up to 180 Minutes Following Two Instillations of Study Drug by Where and Whom CVAD Identified as Dysfunctional (Full Analysis Set)	ANT007	Same as Table 14.2.2.4.1	Same as Table 14.2.2.4.1
Table 14.2.2.4.11	Summary and Statistical Analysis of Proportion of Subjects with Treatment Success Up to 180 Minutes Following Two Instillations of Study Drug by Duration of CVAD Dysfunction (Full Analysis Set)	ANT007	Same as Table 14.2.2.4.1	Same as Table 14.2.2.4.1
Table 14.2.2.5.1	Summary and Sensitivity Analysis of Proportion of Subjects with Treatment Success Up to 180 Minutes Following Two Instillations of Study Drug - Logistic Regression Model (Full Analysis Set)	ANT004	- Same as Table 14.2.1.5.1. - Timepoints to be presented: 120, 150 and 180 mins.	Same as Table 14.2.1.5.1
Table 14.2.2.5.2	Summary and Sensitivity Analysis of Proportion of Subjects with Treatment Success Up to 180 Minutes Following Two Instillations of Study Drug - Logistic Regression Model (Intention-to-Treat Set)	ANT004	Same as Table 14.2.2.5.1	Same as Table 14.2.2.5.1
Table 14.2.2.5.3	Summary and Sensitivity Analysis of Proportion of Subjects with Treatment Success Up to 180 Minutes Following Two Instillations of Study Drug - Logistic Regression Model (Per-Protocol Set)	ANT004	Same as Table 14.2.2.5.1	Same as Table 14.2.2.5.1

Table Number	Table Title	Template Code	Notes	Footnotes/Source Listing Number
Table 14.2.3.1	Rate of Recurrent Catheter Dysfunction Within 30 Days (Full Analysis Set)	TPT005	
Parameters to display:
 
 
- Number (%) of Subjects with Treatment Success [2]
 
- Number (%) of Subjects with Re-Occlusion [3]
 
- Number (%) of Censored Subjects [3]
 
- Time to Re-Occlusion (Days):               
 
- 25th Percentile (95% CI)
 
- Median (95% CI)
 
- 75th Percentile (95% CI)
 
 
 
- Probability of Re-Occlusion Free at Day 30 (95% CI)
 
- Treatment Comparison vs Placebo [4]               
 
- Hazard Ratio (95% CI) [to be displayed in CUSA-081 and Alteplase columns]
 
 
 
- Treatment Comparison vs Alteplase [4]               
 
- Hazard Ratio (95% CI) [to be displayed in CUSA-081 column]
 
 
 
	
Source: Listing 16.2.6.4
 
Footnotes:
 
[1] Time to re-occlusion (Days) = (date of start of first re-occlusion – date of first treatment success + 1). If no re-occlusion the subject is censored to the CVAD removal or study discontinuation/completion date, whichever is the earliest.
 
[2] Percentages are based on the number of subjects in the FAS.
 
[3] Percentages are based on the number with treatment success.
 
[4] Based on Cox proportional hazards model including treatment as a fixed effect.

Table 14.2.3.2 ***	SAS Output: Rate of Recurrent Catheter Dysfunction Within 30 Days (Full Analysis Set)		Raw SAS output	

Table Number	Table Title	Template Code	Notes	Footnotes/Source Listing Number
